7.2 Handling of Missing Data

7.2.1 Handling of Missing or Partial Dates

7.2.1.1 Imputation rules for missing or partial AE start date:

If only Day of AE start date is missing:

If the AE start year and month are the same as that for the first dose date (date of titration visit 6), then:

- If the full (or partial) AE end date is NOT before the first dose date (date of titration visit 6) or AE end date is missing, then impute the AE start day as the day of first dose date (titration visit 6); otherwise, impute the AE start day as 1.
- Otherwise, impute the AE start day as 1.

If Day and Month of AE start date are missing:

If AE start year = first dose year (year of titration visit 6), then:

- If the full (or partial) AE end date is NOT before the first dose date (date of titration visit 6) or AE end date is missing, then impute the AE start Month and Day as the Month and Day of first dose date (date of titration visit 6); otherwise, impute the AE start Month as January and the Day as 1.
- Otherwise, impute the AE start MONTH as January and the DAY as 1.

If Year of AE start date is missing:

If the year of AE start is missing or AE start date is completely missing then query site with no imputation. Also compare the full (or partial) AE end date to the first dose date (date of titration visit 6). If the AE end date is before the first dose date (date of titration visit 6) then the AE should be considered as a pre-treatment AE. Otherwise, the AE will be considered as TEAE.

Compare the imputed AE start date with the treatment-emergent period to determine whether the AE is pre-treatment AE, TEAE (Treatment Emergent Adverse Event) or post-treatment AE.

7.2.1.2 Imputation rules for missing or partial medication start/stop dates:

Missing or partial medication start date:

- If only DAY is missing, use the first day of the month.
- If DAY and Month are both missing, use the first day of the year.
- If DAY, Month and Year are all missing, use a date before the first dose date (date of titration visit 6).

Missing or partial medication stop date:

- If only DAY is missing, use the last day of the month.
- If DAY and Month are both missing, use the last day of the year.

If DAY, Month and year are all missing, assign 'continuing' status to stop date

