- Collect a blood sample for:
 - Complete chemistry panel
 - Liver Chemistry Panel
 - Hematology
 - DNA sample (to be obtained under a separate informed consent for the purposes of biobanking to assess genetic variants associated with hepatic abnormalities [if and when feasible]. This may be obtained at any later visit if the subject initially declines permission but agrees at a later time.)
- Collect a plasma sample for measurement of lixivaptan. Note date and time of sample on the requisition form. The sample must be collected before the first dose of lixivaptan is administered.
- Perform a 12-lead ECG
- If all study entry criteria are met, contact the IRT to complete subject's participation in the Baseline Period, obtain kit assignment, and enter the subject into the Titration Period and proceed as follows:
 - Dispense lixivaptan (Level 1) and have subject take the first dose when they return home from the clinic. Instruct the subject to take 1 capsule twice a day approximately 10 hours apart, e.g., 8 AM and 6 PM.

- Educate the subject to expect aquaretic effects and to maintain fluid intake to prevent dehydration.
- Provide subject with a urine collection container and written instructions to produce a first morning, fasting (8 hours except for water) spot urine specimen to be brought in at Titration Period Visit 6 or provided to the HHC if the visit will be conducted remotely for specific gravity and U_{osm} determination.
- Schedule the subject for Visit 6 to occur in 1 week. Provide the subject with an appointment reminder card and any written instructions.
- If the subject does not meet the study entry criteria, contact the IRT to discontinue the subject. No follow-up visit is needed unless an SAE is ongoing.

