7.3.8.2 Eliciting and Documenting Adverse Events and Serious Adverse Events

All SAEs will be recorded from the time the ICF is signed until study completion. Non-serious AEs will be recorded from the start of study treatment until study completion. Other changes in health or new symptoms occurring during the Screening or Baseline Periods will be recorded as medical history.

At every study visit, subjects will be asked a standard non-leading question to elicit any medically related changes in their well-being. They will also be asked if they have been hospitalized, had any accidents, used any new medications, or changed concomitant medication regimens (both prescription and over-the-counter medications).

In addition to subject observations, any abnormal laboratory test results (hematology, clinical chemistry, or urinalysis) or other safety assessments (e.g., ECGs, radiological scans, vital sign measurements, physical examination findings), including those that worsen from baseline, deemed to be CS in the medical and scientific judgment of the Investigator are to be recorded as AEs or SAEs.

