After obtaining Informed consent, screening assessments will be performed at Visit 1 to determine subject eligibility. Subjects whose anti-hypertensive medications in the absence of diuretics are known and documented to have been stable (unchanged) for at least 3 weeks prior to Visit 1 may proceed to Visit 2 in 1 week to confirm eligibility. Subjects for whom the stability of anti-hypertensive medications in the absence of diuretics is unknown or not documented must be observed for 3 weeks during the Screening Period to ensure stable dosing of anti-

hypertensive medications then will be scheduled for Visit 2.. For those subjects who need to be discontinued from diuretic therapy and/or have their anti-hypertensive therapy optimized, the Screening Period may be extended up to a total of 8 weeks prior to Visit 2.

Subjects who meet all the inclusion criteria and none of the exclusion criteria and achieve stability of background anti-hypertensive medications in the absence of diuretics will return to the clinic for end-of-screening assessments at Visit 2, including body weight, vital signs, and a Complete Chemistry Panel (only if blood pressure medications were adjusted) at Visit 2 (which may be conducted remotely by a home healthcare clinician [HHC] with telemedicine to determine final eligibility). Eligible subjects will then enter the Baseline Period immediately at the completion of Visit 2. Subjects who fail inclusion/exclusion criteria because of temporary or correctable reasons may be re-screened up to 2 times after obtaining new informed consents with the approval of the medical monitor and sponsor.

Baseline Period (Visits 3 – 5): Following completion of all screening assessments and establishment of background medication stability, subjects will enter the 3-week no-study-drug Baseline Period during which time liver chemistry tests and serum creatinine (for eGFR calculation) will be assessed weekly to obtain baseline measurements and assess individual variability. Baseline trough spot urine specific gravity (as a point-of-care surrogate for urine osmolality) and U_{osm} will be determined only at Visit 5. Visits 3 and 4 may be conducted remotely by a HHC. At the successful completion of the Baseline Period (Visit 5), subjects will be dispensed study drug and begin treatment. This completes the Baseline Period and subjects will enter the Titration Period.

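### SAP 7.2.1.1 dates the first dose at Visit 6 although dosing starts on the day of Visit 5, so some first-week AEs with incomplete start dates are classed as pre-treatment (minor)

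*SAP*

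**What the plan says.** SAP 7.2.1.1 links the first-dose date to Visit 6 in three phrasings, each with its own job:

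- **The end-date test:** "If the full (or partial) AE end date is NOT before the first dose date (date of titration visit 6". The same phrase is used to match the AE start month and year, and in the missing-year rule: "AE end date is before the first dose date (date of titration visit 6) then the AE should be considered as a pre-treatment AE".
- **The imputed value:** "impute the AE start day as the day of first dose date (titration visit 6".
- **The year test:** "If AE start year = first dose year (year of titration visit 6".

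If the end date falls before that anchor, a missing start day becomes day 1 of the start month, and a missing day and month become 1 January. The imputed start is then compared with the treatment-emergent period. SAP 7.2.1.2 uses the same anchor once, for medication start dates that are wholly missing.

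The documents put the first dose one visit earlier. Protocol 6.2.3 (Visit 5) says: "Dispense lixivaptan (Level 1) and have subject take the first dose when they return home from the clinic". Visit 6 follows one week later. SAP 3.1 agrees: "At the successful completion of the Baseline Period (Visit 5), subjects will be dispensed study drug and begin treatment".

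**The concern.** Visit 6 closes the first week of treatment; it does not open treatment. An AE that starts and resolves in that week is on drug, but under these rules it ends before the assumed first dose. The imputed start is then pushed back, usually to before the true first dose, and the event drops out of the TEAE tables.

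That conflicts with the TEAE definition in SAP 8.6.5, which runs from exposure to study drug, and with SAP 7.1, where study day and baseline are tied to the first dose. It also conflicts with Protocol 7.3.8.2: "Non-serious AEs will be recorded from the start of study treatment until study completion". A non-serious AE in this study should never be pre-treatment. An SAE could be, because SAEs are collected from consent, so a misclassified first-week SAE would not look odd.

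**Working it through.** The plan gives no figure to reproduce. The check applies 7.2.1.1 literally and asks what share of first-week AEs it calls pre-treatment.

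**Inputs and assumptions.** First dose on day D, the day of Visit 5 (Protocol 6.2.3). Visit 6 on D + g, with g = 7 and a range of 4 to 10 (weekly visits, ±3 days). The AE starts and ends between D and D + g − 1. D is uniform over the 1,461 dates of 2021–2024, which contain 48 month starts and 4 year starts. The SAP gives no calendar start for the treatment-emergent period, so it is taken from D, following SAP 8.6.5.

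**Complete end date.** The end date is always before Visit 6.

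- Start year or whole date missing: classed as pre-treatment directly, 100%.
- Only the day missing: start set to day 1 of the start month. The AE stays a TEAE only if that day 1 falls between D and onset.
- Day and month missing: the same, with 1 January in place of day 1.

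So the share classed as pre-treatment is 1 − k × m / 1,461. Here m = 48 (day missing) or 4 (day and month missing), and k is the average number of days from D to onset, counting both. With each onset day weighted equally (a), k = (g + 1)/2. With each onset/end pair weighted equally (b), k = (g + 2)/3. At g = 7:

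- (a) k = 4: 1 − 4 × 48/1,461 = 86.9%; 1 − 4 × 4/1,461 = 98.9%
- (b) k = 3: 1 − 3 × 48/1,461 = 90.1%; 1 − 3 × 4/1,461 = 99.2%

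Full enumeration of all date pairs gives the same values:

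| Complete end date; missing from start date | g = 4 (a / b) | g = 7 (a / b) | g = 10 (a / b) |
|---|---|---|---|
| Day | 91.8 / 93.4% | 86.9 / 90.1% | 81.9 / 86.9% |
| Day and month | 99.3 / 99.5% | 98.9 / 99.2% | 98.5 / 98.9% |
| Year or whole date | 100% | 100% | 100% |

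If the treatment-emergent period were itself started at Visit 6, every cell would be 100%.

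**Other end-date patterns.** The effect is much smaller. Ranges cover g = 4 to 10 and both weightings.

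| End date | Start day missing | Start day and month missing | Start year or whole date missing |
|---|---|---|---|
| End day also missing | 8–23% | 6–14% | 6–13% |
| Wholly missing | 8–23% | 1–2% | 0% |
| Ongoing or after Visit 6 | 8–18% | about 1% | 0% |

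The 8–18% and 8–23% arise when a month boundary falls between onset and Visit 6: the start month no longer matches the Visit 6 month, so the day is set to 1. Where the start is instead imputed at Visit 6, the AE stays a TEAE with onset 1 to 7 days late (up to 10). The end-day-missing row assumes that a partial end date is compared on its known parts, which the SAP does not specify.

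**Example.** First dose 12 May, Visit 6 on 19 May, AE start recorded as May with no day.

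- Ended 16 May: the end is before 19 May, so the start becomes 1 May and the AE is pre-treatment. This is wrong.
- Ended in May, day unknown: not before the anchor, so the start becomes 19 May. The AE is a TEAE with a late onset.

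**After correction.** With the anchor set to D throughout, 0% are classed as pre-treatment in every pattern, and no imputed onset falls after the end date.

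**The case against.** The strongest reply is that each rule names the first-dose date and adds Visit 6 only in brackets. The rest of the SAP uses actual dosing, so a programmer who takes the recorded dose date gets the right answer. That is true, but the text then offers two anchors that give different TEAE counts, and the bracket is the more specific instruction.

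The second reply is rarity, and it largely stands. The AE must begin and end within 4 to 10 days and have a known end but an incompletely known start. Protocol 7.3.8.2 makes that unlikely: "At every study visit, subjects will be asked a standard non-leading question to elicit any medically related changes in their well-being". The 100% case first triggers a site query. The 99% case needs someone who recalls the exact end day but not the month of onset of an event at most 10 days old. Only the missing-day case is realistic. Programmed edit checks (Protocol 8.8) may resolve others, and a non-serious AE flagged as pre-treatment should look wrong to anyone who knows the collection rule.

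Third, the study stopped early. Only 6 participants entered maintenance (SAP 9), every AE remains in Listing 16.2.7.3, and listings generally show no imputed dates (SAP 8.1). This limits the effect, but Appendix IV still calls for the TEAE overview and the all, serious and non-serious TEAE tables.

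**Conclusion.** The point holds and is minor. The Visit 6 anchor contradicts the protocol and the SAP's own design section, and nothing in either document supports a first dose at Visit 6. For an AE confined to the interval between first dose and Visit 6, with a complete end date, the rule as written gives a pre-treatment label in about 82–93% of cases with only the start day missing, about 99% with day and month missing, and 100% with the year or whole date missing.

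These shares rest on a uniform first-dose calendar date and a literal reading of the rule. They say nothing about how many AEs are affected: the number with incomplete dates is not given and could be zero. Fully dated AEs, laboratory baselines, the HERC-adjudicated hepatic endpoints and the eGFR analysis do not depend on the rule.

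**What to change.** In SAP 7.2.1.1, replace every reference to Visit 6 with the date (or year) of the first lixivaptan dose recorded in the eCRF, or the Visit 5 date if that is missing. Make the same change in 7.2.1.2 for consistency.

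All three phrasings must change: the date used in the tests, the imputed start day and the year test. If only the test date were changed, 13–16% of first-week AEs with a missing start day would still be pre-treatment, and 77% would get an onset after their end date (7-day gap, complete end date).

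The cost is a wording change and one programming anchor. No new data are needed, because Protocol 5.6 already requires dosing dates in the eCRF.

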7.2.2 Handling of Missing Efficacy or Safety Data

If any values of baseline or follow-up eGFR values are missing (i.e. for instance if only two measurements are available then the mean of two measurements will be considered and if in case more than two values are missing the last available measurement will be considered), the remaining available values will be used to determine the baseline or follow-up eGFR. Unscheduled visit values will not be considered for eGFR calculation.

No imputation will be done for any of the safety/PK/PD data.

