The expectation about the efficacy of lixivaptan in ADPKD is supported by the observed clinical effects of lixivaptan on the pharmacodynamic biomarker of urinary osmolality. Clinical studies conducted with lixivaptan in healthy subjects, ADPKD patients, and various other patient populations (patients with hypervolemic and euvoletic hyponatremia) demonstrated that treatment with lixivaptan readily suppresses urinary osmolality to levels below the target threshold of 300 mOsm/kg, irrespective of the specific patient population tested. Importantly, the magnitude of the effect observed with lixivaptan was comparable to the effect observed with tolvaptan in the same patient populations. In addition, like tolvaptan, treatment with lixivaptan was associated with a rapid-onset and fully reversible increase in serum creatinine. Taken together, these results suggest that treatment with lixivaptan can inhibit vasopressin receptor signaling to the extent necessary to observe clinical efficacy of a vasopressin antagonist for the treatment of ADPKD (Devuyst O 2017).¹⁴

Additional background information on the effect of lixivaptan on urine osmolality can be found in the IB.

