4.2.3 Subject Withdrawal Criteria

A subject may withdraw from the study at any time at his/her own request or may be withdrawn at any time at the discretion of the Investigator for safety, behavioral, or administrative reasons.

Subjects who discontinue or are discontinued after the Baseline Period will be considered as a withdrawal, regardless of whether they have received study drug. A subject that withdraws from study drug will be treated as a study withdrawal unless they are being followed for safety reasons.

All premature discontinuations and their causes must be carefully documented in the eCRF, and in the AE form (if applicable).

Subjects not completing the entire study on study drug should be encouraged to continue with the visit schedule, a modified visit schedule, or telephone follow-up as agreed between the subject and the Investigator. At a minimum, subjects should be encouraged to complete the Early Termination Visit (Visit 24 – in the clinic) at the time of study drug discontinuation and the Follow-up Visits (Visits 25 – 27) over the 4 weeks after the last dose of study drug. Subjects with ongoing SAEs or AEs believed to be at least possibly related to study medication will continue to be followed until resolution or for 28 days as warranted by the nature of the AE. If the AE is related to abnormal liver chemistry test results, see [Section 7.3.7](#) for additional follow-up requirements.

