8.5 Efficacy Analysis

Descriptive statistics (n, mean, SD, median, minimum, and maximum) will be presented for observed values at baseline and endpoint, as well as change from baseline in eGFR at the endpoint. Baseline eGFR is defined as the mean of the 3 eGFR assessments obtained during the Baseline Period. However, if any values are missing, the remaining values will be used to determine the baseline eGFR. The endpoint eGFR is defined as the mean of 3 eGFR assessments obtained during the Follow-up Period. However, if any values are missing, the remaining values will be used to determine the endpoint eGFR.

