6.2 Safety Population

The Safety Population is a subset of the Enrolled Population defined as those enrolled subjects who received at least 1 dose of lixivaptan. This population will be utilized for all safety analyses.

6.3 **Efficacy Population**

The Efficacy Population is a subset of the Safety Population defined as those subjects who have at least 1 eGFR determination during the Baseline Period and have at least 1 eGFR determination during the Follow-up Period. This population will be used for efficacy analyses.

6.4 **Pharmacokinetic (PK) Population**

The Pharmacokinetic (PK) Population is a subset of the Safety Population defined as those subjects who had at least 1 on-therapy evaluable PK measurement.

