7 STATISTICAL CONSIDERATIONS AND ANALYSIS

7.1 Derived General Variables

The below table (Table 4) provide the list of derived variables for demographic and baseline characteristics, various duration derivations, drug compliance, baseline derivations and other important derivations applicable for this study.

Variables	Formula					
Demographic characteristics						
Age at informed consent (in years)	Age = year of informed consent – year of birth					
BMI (kg/m ²)	weight (kg)/[height (m)] 2					
Derivation of Duration						
Study Duration (Days)	(Date of Last Visit – Date of informed consent) + 1					
Study day at any visit	Date of interest – date of first dose of study drug. One day is added if this difference is ≥ 0					
Adverse event duration (in days)	Event end date - Event onset date + 1.					
Duration of Exposure						
Duration of Exposure (days) in Titration Period	(Date of last administration of study drug – Date of first administration of study drug) +1, during the 6 week titration period					
Duration of Exposure (days) in Maintenance Period	(Date of last administration of study drug – Date of first administration of study drug) +1, during the 52 week maintenance period					
Treatment Compliance						
Treatment Compliance	(Total No. of capsules dispensed – Total No. of capsules returned)*50/total assigned dose*100 where, total assigned dose will be derived by sum of (AM+PM dose)*duration of this dose level for all different dosing levels					
eGFR Baseline and Fin	al Assessment Derivation (Appendix I)					
Baseline eGFR	Mean of 3 eGFR assessments (Visit 3, Visit 4 & Visit 5) obtained during the baseline period					
Final Assessment eGFR	Mean of 3 eGFR assessments (Visit 25, Visit 26 & Visit 27) obtained during the follow-up period					
Baseline Derivations						

Table 4: Derived Variables

Baseline	Latest non-missing measurement prior to first dose of study drug administration	
Change from baseline	Test Value at Post baseline value – Baseline Value	
Geometric Coefficient of Variation (CV%) for Pharmacokinetic data		
Geometric CV%	CV (%) =100× $\sqrt{\exp(\hat{\sigma}^2) - 1}$, where $\hat{\sigma}^2$ denotes the variance of the natural log-transformed values.	
	the natural log-transformed values.	

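### SAP 7.2.2: the fallback for missing eGFR applies only when a window is empty, so it must take a value from outside that window (minor correction)

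*SAP*

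**What the plan says.** SAP 7.1 defines baseline eGFR as the mean of Visits 3, 4 and 5, and the final assessment as "Mean of 3 eGFR assessments (Visit 25, Visit 26 & Visit 27) obtained during the follow-up period".

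SAP 7.2.2 deals with gaps. Its main clause says that "the remaining available values will be used to determine the baseline or follow-up eGFR". A parenthesis inside that sentence gives two cases. With two measurements available, their mean is taken; and "if in case more than two values are missing the last available measurement will be considered". The next sentence adds: "Unscheduled visit values will not be considered for eGFR calculation".

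Protocol 8.5 has one rule for the endpoint: "if any values are missing, the remaining values will be used to determine the endpoint eGFR". It says the same for baseline. It has no carry-forward and does not exclude unscheduled values.

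SAP 6.3 limits the Efficacy Population to treated subjects who "have at least 1 eGFR determination during the Baseline Period" and at least one in the Follow-up Period. It does not say whether an unscheduled determination counts. SAP 8.7 bases the efficacy analyses on this population.

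On timing, the notes to SAP Table 3 put Visit 25 no earlier than the 8th day after the last dose and tie the last dose to V24. They list V24/ET as the last scheduled chemistry panel before follow-up. Protocol 1.4 reports that "treatment with lixivaptan was associated with a rapid-onset and fully reversible increase in serum creatinine".

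**The concern.** A rule for missing values in a three-value window should say what happens with two, one and no values. The SAP's second case is set at more than two missing, which leaves nothing in the window. Whatever measurement is then the last available was taken outside the window that SAP 7.1 defines.

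For follow-up this matters because the three visits are placed off drug, while the last scheduled creatinine before them is taken at the end of dosing. If that value stood in for the endpoint, a reversible drug effect on creatinine would be read as loss of renal function. It would fall on subjects with incomplete follow-up, many of whom would be early stoppers.

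For baseline, the substitute would be a Screening value. That is taken before any lixivaptan, so no drug effect enters, but it is still not the V3–V5 baseline.

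**Working it through.** The plan gives no figure to reproduce here: the sample size rests on analogy with another study, and eGFR has no stated effect size or SD. The check is a reading of the rule, then a scale.

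**Step 1: when the clause applies.** Three visits, each present or missing, give 2³ = 8 patterns for V25, V26 and V27.

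| Values missing | Patterns | More than two missing? | Scheduled follow-up eGFR present? | Value used |
|---|---|---|---|---|
| 0 | 1 | no | yes | mean of three |
| 1 | 3 | no | yes | mean of two |
| 2 | 3 | no | yes | the one remaining |
| 3 | 1 | yes | no | last available, from outside the window |

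The clause operates in one pattern of eight.

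**Step 2: what it contradicts in that pattern.**
- The main clause of SAP 7.2.2 uses remaining values, and there are none.
- SAP 7.1 names V25–V27.
- SAP 8.7.1.1 takes the final assessment from the follow-up period.
- Protocol 8.5 uses remaining values only.

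**Step 3: whether such a subject is analysed.** With V25–V27 all missing there is no scheduled follow-up eGFR, so SAP 6.3 excludes the subject. The exception is a subject whose only follow-up eGFR is unscheduled. SAP 6.3 as worded can admit that value, 7.2.2 bars it from the calculation, and the clause then points back to an earlier scheduled value, normally V24/ET. Protocol 4.2.3 allows early stoppers "a modified visit schedule, or telephone follow-up as agreed" between subject and investigator, so such a draw is possible.

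**Step 4: the baseline side.** Enrolment requires completing Visit 3 (SAP 6.1), where creatinine is drawn. An empty baseline window therefore needs an unusable V3 sample and nothing usable at V4 or V5. SAP 8.4 summarises baseline eGFR for the Enrolled Population, which does not itself require an eGFR.

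**Step 5: scale.** The CKD-EPI equation in SAP Appendix I has exponent −1.209 for creatinine above κ. If creatinine rises by a fraction r on drug, eGFR falls by 1 − (1 + r)^−1.209. The documents call the rise mild (protocol 4.2.4) and give no size, so r is an assumption. An off-drug eGFR of 50 is also assumed. The shift in the mean is the per-subject fall times the share of subjects affected.

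| Assumed r | 1 − (1 + r)^−1.209 | Fall per subject at eGFR 50 | Mean shift, 2% affected (1 of 50) | Mean shift, 20% affected |
|---|---|---|---|---|
| 5% | 5.7% | 2.9 | −0.06 | −0.57 |
| 10% | 10.9% | 5.4 | −0.11 | −1.09 |
| 15% | 15.5% | 7.8 | −0.16 | −1.55 |

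Units are mL/min/1.73 m². The 20% column is a stress case; nothing in the documents suggests so many.

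**Step 6: with the clause removed.** The seven patterns with at least one scheduled value give an in-window endpoint. The eighth gives none. No earlier value can enter.

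**The case against.** The strongest reply is that the clause is a slip. The sentence goes from two values available to the next case, which would naturally be one value available. Read as two missing, the last available measurement is simply the single remaining in-window value, and the SAP agrees with protocol 8.5. That is plausible and the main clause supports it. The edit is still needed, because a programmer who follows the text as written would carry a value forward.

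A reader might infer that the SAP puts an on-drug eGFR in place of the off-drug endpoint for early stoppers generally. The documents do not support that, for three reasons.
- The SAP never says from which period the substitute comes. That it is on drug is inferred from the visit schedule, and it fails for a subject who stops drug but keeps attending scheduled visits, as protocol 4.2.3 encourages.
- The Efficacy Population removes subjects with no follow-up eGFR.
- Protocol 4.2.3 asks early stoppers, at a minimum, to complete V24/ET and Visits 25–27. Nothing says that a redraw or a modified-schedule draw is coded as unscheduled.

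Barring unscheduled values is not an error in itself. SAP 8.1 keeps them out of all summary tables, and averaging every draw could over-weight retests done for cause. A discarded redraw brings in no outside value while another scheduled value remains. One could also read 7.2.2 as meaning that unscheduled values do not count for the population either, but SAP 6.3 does not say so.

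On baseline, SAP 4.2.2 itself speaks of determinations from Screening and Baseline, so a Screening value is not foreign to every statement of the endpoint. It is foreign to SAP 7.1 and protocol 8.5.

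Finally, Section 9 records early termination with only 6 participants in maintenance and says that no statistical analyses will be done. Appendix IV lists no eGFR change table, and even as planned the endpoint was descriptive. This stands for follow-up. It does not fully cover baseline, because Appendix IV keeps Table 14.1.2.2.1 on baseline disease characteristics and Listing 16.2.4.2.1 on baseline eGFR.

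**Conclusion.** The clause is wrong as written: it can apply only to an empty window and then reaches outside it, against SAP 7.1, its own main clause and protocol 8.5. The practical reach is small. For follow-up it needs a subject whose sole follow-up eGFR is unscheduled; for baseline it needs a window with no usable sample.

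In an affected subject the error could be about 3 to 8 mL/min/1.73 m² (assumed creatinine rise 5% to 15%, eGFR 50, creatinine above κ, V24/ET on drug). One such subject in 50 would move the mean by 0.06 to 0.16. With a descriptive endpoint and no change table in the reduced output, this is a minor correction and does not threaten the trial's conclusions.

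**What to change.** In SAP 7.2.2, delete the clause on more than two missing values. State instead that the baseline or endpoint eGFR is the mean of the available in-window values, that one value suffices, and that an empty window gives no baseline or endpoint value and no change score.

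Then apply one rule on unscheduled values to both SAP 6.3 and 7.2.2. One workable form: an unscheduled central-laboratory value, drawn pre-dose in the Baseline Period or from day 8 off drug through V27, is used only to replace a missing scheduled value in that window, and otherwise counts neither for the population nor for the calculation. If unscheduled values are to stay out altogether, 6.3 should require a scheduled determination.

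The cost is one paragraph in 7.2.2, a line in 6.3 and, if replacements are allowed, a cross-reference in 7.1 and a stated exception to the convention in 8.1. No new data are needed, and the missing-value rule in protocol 8.5 can stay as it is.
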